6.2.1.5. Ocular Events

An ophthalmologist should evaluate visual complaints (eg, uveitis, retinal events).

For specific management guidelines, please see [Attachment 7](#).

6.2.1.6. Immune-Related Myocarditis

Immune-related myocarditis has been associated with the administration of atezolizumab. Immune-related myocarditis should be suspected in any subject presenting with signs or symptoms suggestive of myocarditis, including, but not limited to, dyspnea, chest pain, palpitations, fatigue, decreased exercise tolerance, or syncope. Immune-related myocarditis needs to be distinguished from myocarditis resulting from infection (commonly viral, eg, in a subject who reports a recent history of gastrointestinal illness), ischemic events, underlying arrhythmias, exacerbation of pre-existing cardiac conditions, or progression of malignancy.

All subjects with possible myocarditis should be evaluated urgently by performing cardiac enzyme assessment, an ECG, a chest X-ray, an echocardiogram, and a cardiac MRI as appropriate per institutional guidelines. A cardiologist should be consulted. An endomyocardial biopsy may be considered to enable a definitive diagnosis and appropriate treatment, if clinically indicated. Subjects with signs and symptoms of myocarditis, in the absence of an identified alternate etiology, should be treated according to the guidelines in [Attachment 7](#).

6.2.1.7. Pancreatic Events

Symptoms of abdominal pain associated with elevations of amylase and lipase, suggestive of pancreatitis, have been associated with the administration of atezolizumab. The differential diagnosis of acute abdominal pain should include pancreatitis. Appropriate work-up should include an evaluation for ductal obstruction, as well as serum amylase and lipase tests.

For specific management guidelines, please see [Attachment 7](#).

6.2.1.8. Dermatologic Events

Treatment-emergent rash has been associated with atezolizumab. The majority of cases of rash were mild in severity and self-limited, with or without pruritus. A dermatologist should evaluate persistent or severe rash or pruritus. A biopsy should be considered unless contraindicated.

For specific management guidelines, please see [Attachment 7](#).

6.2.1.9. Neurologic Disorders

Myasthenia gravis, Guillain-Barré syndrome, and meningoencephalitis have been observed with single agent atezolizumab. Subjects may present with signs and symptoms of sensory or motor neuropathy. Diagnostic work-up is essential for an accurate characterization to differentiate between alternate etiologies.

For specific management guidelines, please see [Attachment 7](#).

6.2.1.10. Immune-Related Meningoencephalitis

Immune-related meningoencephalitis is an identified risk associated with the administration of atezolizumab. Immune-related meningoencephalitis should be suspected in any subject presenting with signs or symptoms suggestive of meningitis or encephalitis, including, but not limited to, headache, neck pain, confusion, seizure, motor or sensory dysfunction, and altered or depressed level of consciousness. Encephalopathy from metabolic or electrolyte imbalances needs to be distinguished from potential meningoencephalitis resulting from infection (bacterial, viral, or fungal) or progression of malignancy, or secondary to a paraneoplastic process. All subjects being considered for meningoencephalitis should be evaluated urgently with a CT scan and/or MRI scan of the brain to evaluate for metastasis, inflammation, or edema. If deemed safe by the treating physician, a lumbar puncture should be performed and a neurologist should be consulted. For specific management guidelines, please see [Attachment 7](#).

6.2.1.11. Immune-related Nephritis

Immune-related nephritis is an identified risk associated with the administration of atezolizumab. Immune-related nephritis is a relatively rare complication of checkpoint inhibitor therapy with the most common reported underlying pathology being acute tubulo-interstitial nephritis (ATIN). The most common presentation is asymptomatic increase in creatinine levels. In the absence of alternative etiologies (eg, prerenal and postrenal causes, and concomitant medications), immune-related nephritis is defined as renal dysfunction requiring steroids treatment and/or confirmed by biopsy. For specific management guidelines, please see [Attachment 7](#).

6.2.1.12. Systemic Immune Activation

Systemic immune activation is a rare condition characterized by an excessive immune response. Given the mechanism of action of atezolizumab, systemic immune activation is considered a potential risk when given in combination with other immunomodulating agents. Systemic immune activation should be included in the differential diagnosis for subjects who, in the absence of an alternate etiology, develop a sepsis-like syndrome after administration of atezolizumab, and the initial evaluation should include the following:

- Complete blood count (CBC) with peripheral smear
- Prothrombin time (PT), partial thromboplastin time (PTT), fibrinogen, and D-dimer
- Ferritin
- Triglycerides
- AST, ALT, total bilirubin
- Lactate dehydrogenase (LDH)
- Complete neurologic and abdominal examination (assess for hepatosplenomegaly)
- Serum sample for cytokine analysis

If systemic immune activation is still suspected after the initial evaluation, atezolizumab should be withheld with the provision of appropriate supportive medical care, including corticosteroid therapy. The Sponsor should be contacted for additional recommendations.

For specific management guidelines, please see [Attachment 7](#).

6.3. Management of Infusion-related Reactions

6.3.1. Infusion-related Reactions

Subjects should be observed carefully during infusions. Trained study staff at the clinic should be prepared to intervene in case of an IRR, and resources necessary for resuscitation must be available. Attention to staffing should be considered when multiple subjects will be dosed at the same time.

For infusion reactions of any grade/severity, immediately interrupt the daratumumab infusion and manage symptoms. Management of infusion reactions may require reduction in the rate of infusion, or discontinuation of daratumumab (see [Table 10](#)).

Table 10: Management Guidelines for Daratumumab Infusion-related Reactions

Severity	Management
Grade 1-2 (mild to moderate)	Once reaction symptoms resolve, resume the infusion at no more than half the rate at which the reaction occurred. If the subject does not experience any further reaction symptoms, then infusion rate escalation may resume at increments and intervals as clinically appropriate up to the maximum rate of 200 mL/hr (see Table 7).
Grade 3 (severe)	Once reaction symptoms resolve, consider restarting the infusion at no more than half the rate at which the reaction occurred. If the subject does not experience additional symptoms, then resume infusion rate escalation at increments and intervals as outlined in Table 7 . Repeat the procedure above in the event of recurrence of Grade 3

Grade 4 (life threatening)	symptoms. Permanently discontinue daratumumab if the subject experiences a \geq Grade 3 infusion-related symptom at the subsequent infusion. Permanently discontinue daratumumab treatment.
-------------------------------	--

IRR = infusion-related reaction; IV = intravenous.

6.3.2. Atezolizumab

No premedication is indicated for the administration of atezolizumab in Cycle 1. Subjects who experience an IRR with Cycle 1 of atezolizumab may receive premedication with antihistamines or antipyretics/analgesics (eg, acetaminophen) for subsequent infusions. Metamizole (dipyrone) is prohibited in treating atezolizumab associated IRRs, due to its potential for causing agranulocytosis. Table 11 provides management guidelines for atezolizumab IRRs in Cycle 1. For subsequent cycles, infusion-related reactions should be managed according to institutional guidelines.

Table 11: Management Guidelines for Atezolizumab Infusion-related Reactions

Severity	Management
Grade 1	
 Reduce infusion rate to half the rate being given at the time of event onset. After the event has resolved, the investigator should wait for 30 minutes while delivering the infusion at the reduced rate. If tolerated, the infusion rate may then be increased to the original rate.
Grade 2	
 Interrupt atezolizumab infusion. Administer aggressive symptomatic treatment (eg, oral or IV antihistamine, anti-pyretic, glucocorticoids, epinephrine, bronchodilators, oxygen). Restart only after the symptoms have adequately resolved to baseline grade. The infusion rate at restart should be half of the infusion rate that was in progress at the time of the onset of the IRR. At next cycle, administer oral premedication with antihistamine and anti-pyretic and monitor closely for IRR.
Grades 3–4	
 Stop infusion. Proper medical management which may include oral or IV antihistamine, anti-pyretic, glucocorticoids, epinephrine, bronchodilators, and oxygen Discontinue atezolizumab.^a Contact the Sponsor if atezolizumab is discontinued.

IRR = infusion-related reaction; IV = intravenous.

- a. Resumption of atezolizumab may be considered in subjects who are deriving benefit and have fully recovered from the immune-related event. Subjects can be rechallenged with atezolizumab only after approval has been documented by both the investigator (or an appropriate delegate) and the Study Responsible Physician.

7. TREATMENT COMPLIANCE

Study drugs (daratumumab and atezolizumab) will be administered by qualified site staff, and the details of each administration will be recorded in the case report form (CRF). Additional details are provided in the SIPPM.

Beginning with the implementation of Amendment 7, subjects who are deriving clinical benefit from atezolizumab monotherapy, but do not have access to commercial atezolizumab, may continue treatment under the supervision of treating investigators in accordance with local regulatory approvals and standard of care guidelines.^{50,51} Study drug accountability must continue to be monitored and documented by the study site.

8. PRESTUDY AND CONCOMITANT THERAPY

Throughout the study, investigators may prescribe any concomitant medications or treatments deemed necessary to provide adequate supportive care except for those listed in Section 8.2. The Sponsor must be notified in advance (or as soon as possible thereafter) of any instances in which prohibited therapies are administered.

All prior treatments for malignancies, including those since diagnosis, must be recorded at Screening.

Routine systemic use of the following concomitant medications will be collected in the CRF and recorded in the source documents beginning with signing of the ICF to PD or until the start of subsequent anticancer treatment, if earlier: growth factors, transfusions, anti-infectives (antibacterials, antivirals, and antimycotics), corticosteroids, anti-arrhythmics and other cardiac supportive therapy, anti-epileptics, centrally acting psychiatric medication, anti-histamines and other medications targeting postinfusion systemic reactions, bisphosphonates, and any anticancer therapy (including radiation).

The use of concomitant medications used to treat adverse events or infusion-related reactions will be collected in the CRF and recorded in the source documents beginning with the signing of the ICF until PD.

Prestudy therapies administered up to 30 days before first dose of study drug must be recorded at Screening. Concomitant therapies must be recorded throughout the study beginning with start of the first dose of study drug until the end of treatment assessment. Concomitant therapies should also be recorded beyond 30 days after the last dose of study drug only in conjunction with serious adverse events that meet the criteria outlined in Section 12.3.2, Serious Adverse Events.

8.1. Permitted Therapies

Subjects are to receive full supportive care during the study. The following medications and supportive therapies are examples of support therapies that may be used during the study:

- Antivirals (antiviral prophylaxis should be considered for the prevention of herpes zoster virus reactivation)
- Granulocyte colony stimulating factors and transfusion of platelets
- Oral contraceptives
- Hormone-replacement therapy
- Palliative radiotherapy (eg, treatment of known bony metastases) provided it does not interfere with the assessment of tumor target lesions (eg, the lesion being irradiated is not the only site of disease, as that would render the subject not evaluable for response by tumor assessments according to RECIST 1.1). It is not a requirement to withhold atezolizumab during palliative radiotherapy; discuss with the Sponsor
- Mineralocorticoids (eg, fludrocortisone)
- Corticosteroids are allowed for the treatment of immune-related adverse events, infusion-related reactions, and as pre-infusion or pre-injection medication for daratumumab. Acute use of systemic corticosteroids >10 mg/day prednisone equivalent, or acute use of higher equivalent doses may be allowed with Sponsor approval.

Other symptoms may be managed according to institutional guidelines provided prohibited therapies are not administered (see Section 8.2).

Premedication with antihistamines may be administered for any atezolizumab infusions after Cycle 1.

In general, investigators should manage subject care with supportive therapies as clinically indicated per local standards. Subjects who experience infusion-associated symptoms may be treated symptomatically with acetaminophen, ibuprofen, diphenhydramine, or famotidine or another H₂ receptor antagonist per standard practice (for sites outside the United States, equivalent medications may be substituted per local practice). Serious infusion-associated events manifested by dyspnea, hypotension, wheezing, bronchospasm, tachycardia, reduced oxygen saturation, or respiratory distress should be managed with supportive therapies as clinically indicated (eg, supplemental oxygen and β_2 -adrenergic agonists).

8.2. Prohibited Therapies

Use of the treatments listed below is prohibited during the study:

- Other agents that target CD38, PD-1 or its ligand, PD-L1.
- Any concomitant therapy intended for the treatment of cancer, including NSCLC, whether health authority–approved or experimental, is prohibited for various time periods prior to starting study treatment, depending on the anti-cancer agent (see Section 4.2), and during study treatment until disease progression is documented and subject has discontinued study treatment. This includes but is not limited to chemotherapy, hormonal therapy, immunotherapy, radiotherapy, investigational agents, or herbal therapy (unless otherwise noted).
- Denosumab; subjects who are receiving denosumab prior to enrollment must be willing and eligible to receive a bisphosphonate instead while in the study.
- Dipyrrone (metamizole)
- Any live, attenuated vaccine (eg, FluMist®) within 4 weeks prior to administration of study drug or during treatment or within 5 months following the last atezolizumab dose.

The Sponsor must be notified in advance (or as soon as possible thereafter) of any instances in which prohibited therapies are administered.

9. STUDY EVALUATIONS

9.1. Study Procedures

9.1.1. Overview

The Time and Events Schedule (Table 1) summarize the frequency and timing of assessments applicable to this study.

Additional serum or urine pregnancy tests may be performed, as determined necessary by the investigator or required by local regulation, to establish the absence of pregnancy at any time during the subject's participation in the study. Repeat or unscheduled samples may be taken for safety reasons or for technical issues with the samples.

As of Amendment 6, subject screening and enrollment has been terminated, combination treatment will be discontinued, and subjects will be given the option to receive atezolizumab monotherapy, following the treatment procedures for Arm A (Section 6.2). Limited data collection will subsequently be performed, see Section 9.2.

9.1.2. Optional Prescreening Phase

The optional Prescreening Phase, which will include a separate informed consent, will allow for the collection of archival formalin-fixed paraffin-embedded (FFPE) tumor tissue to be submitted for PD-L1 determination using the SP142 assay, before the formal screening process for the full study. Given the inter-assay differences in PD-L1 determination, these results can help determine the likelihood of eligibility for study participation, prior to signing of informed consent for study participation (Hirsch 2016)²¹. Unless the archival tumor sample used in the Prescreening Phase was obtained after completion of the most recent line of therapy with no intervening therapies and is less than 1 year old, the subject will be required to have a fresh biopsy performed during the Screening Phase (Section 9.6.1 Tumor Tissue Samples), which will be used to formally determine study eligibility based on tumor cell PD-L1 status. Archival PD-L1 staining may not correlate with PD-L1 staining using a fresh tumor specimen.

9.1.3. Screening Phase

The Screening Phase begins with the signing of the ICF, which must be obtained before any study-specific procedures are performed (except for tumor imaging assessments that were performed as part of the subject's routine standard of care). The screening for PD-L1 status may occur within 56 days prior to first administration of study drug. Tumor samples must meet the same requirements as outlined in Section 9.6.1. All other screening procedures must be performed only after PD-L1 results are available, and within 28 days before the first administration of study drug. For subjects who do not meet Inclusion Criterion 5, no further Screening procedures should be performed. The Screening Phase may be extended by a maximum of 14 days in situations in which screening procedures require repetition or PD-L1 results are not available, after consultation with the Sponsor. However, screening procedures, including standard of care tumor imaging assessments, must be performed within 28 days of first administration of study drug. During the Screening Phase, eligibility criteria will be reviewed and a complete clinical evaluation will be performed as specified in the Time and Events Schedule (Table 1). Subjects were initially stratified based on PD-L1 status (IC0 and TC0 vs. others), based on central laboratory assessment (using the Ventana Medical Systems, Inc. PD-L1 [SP142] assay), and histology (squamous vs. non-squamous), as well as number of previous lines of therapy (1 or >1), see Section 5 for the current stratification procedures. Screening procedures will be performed within 28 days before enrollment. Subjects may be retested for laboratory values that do not meet eligibility criteria within the 28-day Screening Phase.

If a subject does not meet all inclusion and exclusion criteria (is a screen failure) but at some point in the future is expected to meet the subject eligibility criteria, the subject may be rescreened on 1 occasion. Subjects who are rescreened will be assigned a new subject number, undergo the informed consent process, and then restart a new Screening Phase.

9.1.4. Open-Label Treatment Phase

Details of the procedures performed during the Treatment Phase are outlined in the Time and Events Schedule (Table 1). Subjects in the randomized phase should start study treatment within 72 hours after randomization. A window of ± 1 day for Cycles 1 to 3 for subjects receiving daratumumab and ± 3 days for all other drug administration visits is allowed for drug

administration visits to the clinic. Clinical evaluations and laboratory studies may be repeated more frequently than outlined in the Time and Events Schedule, if clinically indicated. If treatment is discontinued, the subject will complete the End-of-Treatment assessment, and enter the Follow-up Phase.

End of Treatment

Unless a subject withdraws consent for study participation or is lost to follow up, an End-of-Treatment Visit is to occur at 30 days after the last dose of study treatment. A delay of this visit to up to 7 days is permitted. Every effort should be made to conduct the End-of-Treatment Visit before the subject starts subsequent treatment. If a subject is unable to return to the site for the End-of-Treatment Visit, then the subject should be contacted to collect information on Grade 2 or higher adverse events and concomitant medications used to treat Grade 2 or higher adverse events, any immune-related AE, or any infusion-related reactions until disease progression. Additional information on reporting of AEs is presented in Section 12.

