Adverse events ^b		Continuous from ICF through 30 days (or 90 days for SAEs) after the last dose of study drug or start of subsequent anticancer therapy, if earlier (see Section 12.3.1)									
Prior and Concomitant Medications		Continuous 30 days prior to 1st administration of study drug through 30 days after last dose of study drug									
Survival and subsequent anti-cancer therapy											X

AE=adverse event, C=cycle, CRF=case report form, COPD=chronic obstructive pulmonary disease, CT=computed tomography, D or d=day, ECOG= Eastern Cooperative Oncology Group Performance Status, EOT=end of treatment, FEV-1=forced expiratory volume; maximal amount of air forcefully exhaled in 1 sec., HBV=hepatitis B virus, HCV=hepatitis C virus, IAT=indirect antiglobulin test, ICF=informed consent form, MRI=magnetic resonance imaging, PD=progressive disease, PD-L1=programmed death-ligand 1, Ph=phase, q=every, SIPPM=Site Investigational Product Procedures Manual

- Safety Run-in and Arm B only:** C1D1: measure vital signs immediately before the start of the infusion; at 0.5, 1, 1.5, 2 and 3.5 hrs after the start of the infusion; at the end of the infusion; and 0.5 and 1 hr after the end of the infusion. For all subsequent Safety Run-in and Arm B administrations (daratumumab + atezolizumab), measure immediately before the administration start, at the end of the atezolizumab infusion, and as clinically indicated. **Arm A only:** vital signs should be assessed at Screening, within 24 hrs of the start of each infusion and at the end of each infusion.
- Beginning with the implementation of Amendment 7, only serious adverse events will be reported and entered in the Sponsor safety repository for subjects who continue to be treated according to local regulatory approval and standard of care guidelines.^{50,51}

ABBREVIATIONS

ADCC	antibody dependent cell-mediated cytotoxicity
AE	adverse event
ALK	anaplastic lymphoma kinase
Breg	regulatory B cell
CBC	complete blood count
CBR	clinical benefit rate
CDC	complement-dependent cytotoxicity
COPD	chronic obstructive pulmonary disease
CR, sCR	complete response; stringent complete response
CRF	case report form(s) (paper or electronic as appropriate for this study)
CT	computed tomography
CyTOF	cytometry time of flight
DCF	data clarification form
DLT	dose-limiting toxicity
DMC	Data Monitoring Committee
DoR	duration of response
ECG	electrocardiogram
ECOG	Eastern Cooperative Oncology Group Performance Status

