12.3. Procedures

12.3.1. All Adverse Events

All adverse events and special reporting situations will be reported from the time a signed and dated ICF is obtained until 30 days after the last dose of study drug (or 90 days for serious adverse events), or until start of subsequent anticancer therapy or the subject withdraws consent

for study participation, if earlier, which may include contact for follow-up of safety. For subjects who have received subsequent treatment with therapeutic intent for NSCLC during the adverse event reporting period, only adverse events that are considered to be possibly, probably, or definitely related to atezolizumab or daratumumab need to be reported. Serious adverse events, including those spontaneously reported to the investigator, must be reported using the Serious Adverse Event Form. The Sponsor will evaluate any safety information that is spontaneously reported by an investigator beyond the time frame specified in the protocol.

Disease progression should not be recorded as an adverse event or serious adverse event term; instead, signs and symptoms of clinical sequelae resulting from disease progression/lack of efficacy will be reported if they fulfill the serious adverse event definition (refer to Section 12.1.1). Death should not be recorded as an adverse event or serious adverse event, but as the outcome of an adverse event. The adverse event that resulted in the death should be reported as a serious adverse event. All events that meet the definition of a serious adverse event will be reported as serious adverse events, regardless of whether they are protocol-specific assessments. Anticipated events will be recorded and reported as described in [Attachment 4](#).

All adverse events, regardless of seriousness, severity, or presumed relationship to study drug, must be recorded using medical terminology in the source document and the CRF. Whenever possible, diagnoses should be given when signs and symptoms are due to a common etiology (eg, cough, runny nose, sneezing, sore throat, and head congestion should be reported as "upper respiratory infection"). Investigators must record in the CRF their opinion concerning the relationship of the adverse event to study therapy. All measures required for adverse event management must be recorded in the source document and reported according to Sponsor instructions.

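### After a missed End-of-Treatment visit, Protocol 9.1.4 asks for fewer adverse events than 12.3.1 and Table 1 require, and Section 8 disagrees with itself and Table 1 on when collection of medication for adverse events ends

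*Protocol*

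**What the plan says.** Protocol 9.1.4 sets the visit: "an End-of-Treatment Visit is to occur at 30 days after the last dose of study treatment", with up to 7 days' delay allowed. A subject who cannot come back to the site is instead to be "contacted to collect information on Grade 2 or higher adverse events and concomitant medications used to treat Grade 2 or higher adverse events". The sentence goes on with "any immune-related AE, or any infusion-related reactions until disease progression", and the paragraph ends with a pointer: "Additional information on reporting of AEs is presented in Section 12".

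Protocol 12.3.1 has events reported "until 30 days after the last dose of study drug (or 90 days for serious adverse events"), or to the start of subsequent anticancer therapy or withdrawal of consent if earlier. It also states: "All adverse events, regardless of seriousness, severity, or presumed relationship to study drug, must be recorded". The adverse event row of Table 1 gives the same 30-day and 90-day limits.

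On medication, Section 8 says that drugs given for adverse events or infusion-related reactions are "recorded in the source documents beginning with the signing of the ICF until PD". The last paragraph of Section 8 has concomitant therapies recorded up to the end-of-treatment assessment, and later than 30 days after the last dose only in connection with serious adverse events. Table 1 reads: "Continuous 30 days prior to 1st administration of study drug through 30 days after last dose of study drug".

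**The concern.** The safety tables depend on every subject being asked the same question over the same period. SAP 2.6.10 counts an event as treatment-emergent up to 30 days after the last dose, with no grade threshold and no stop at progression, and SAP 6.1.1 tabulates these events, including by worst grade. If a site follows 9.1.4 as written, a subject reached by contact is asked a narrower question than one who attends. Ascertainment of non-serious events then depends on attendance. Section 8 adds a second inconsistency: two sites could stop recording treatment for an adverse event at different times and each point to a protocol sentence in support.

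**Working it through.** No sample size, power or event count is involved, so the check sets the rules side by side.

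Adverse events:

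| Source | Grades | End of collection | Stops at progression? |
|---|---|---|---|
| 9.1.4 contact | Grade 2 or higher; immune-related events and infusion reactions named without a grade | Progression, if the closing phrase governs events; otherwise not stated there | Unclear |
| 12.3.1 | All | 30 days (90 if serious); earlier for new anticancer therapy or withdrawn consent | No |
| Table 1 | No limit | 30 days (90 if serious); earlier for new anticancer therapy | No |
| SAP 2.6.10 | No limit | 30 days, or the day before subsequent therapy; related events count whenever they start | No |

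Medication for adverse events:

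| Source | End of collection |
|---|---|
| 9.1.4 contact | Progression |
| Section 8, sentence on adverse event and infusion-reaction drugs | Progression |
| Section 8, last paragraph | End-of-treatment assessment; later only with serious events |
| Table 1 | 30 days after last dose |

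1. **Grade.** The 9.1.4 threshold differs from 12.3.1 on any reading. The least that is missed is non-serious Grade 1 events that are neither immune-related nor infusion reactions. If the immune-related and infusion-reaction terms are only indications for the medication, Grade 1 events of those kinds are also not asked for as events.

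2. **Stop point.** The closing phrase can attach to the medication list it follows or to the whole sentence. On the first reading the event gap is Grade 1 only. On the second, if progression falls d days after the last dose (d from 0 to 30), the contact does not ask about 30 − d days. For d = 0 that is 30 days; for d = 21, one full cycle, it is 30 − 21 = 9 days. If progression came before the last dose, all 30 days are left out. The documents give no distribution for d, and new anticancer therapy would shorten the 30 days anyway.

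3. **Medication.** The progression stop conflicts with Table 1 and with the last paragraph of Section 8 on either reading. The choice matters most where dosing continues after progression: subjects treated beyond progression with Sponsor approval (9.4.2, Table 12), and Arm A subjects who crossed over after confirmed progression (3.1, 4.3). For them the stop falls before their last doses.

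4. **Rule in force.** Section 12.4 (Amendment 6) excepts Grade 1 to 2 and non-immune-mediated events, and 12.5 (Amendment 7) keeps only serious events. The study report, however, uses the data reviewed on 23 May 2018 (3.2, 17.9.1), before Amendment 6 of 14 August 2018. For those data 12.3.1 was the governing rule.

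5. **What 9.1.4 leaves untouched.** Serious events are reportable within 24 hours (12.3.2) and carry the 90-day limit (12.3.1). Date and cause of death are collected in follow-up (9.1.5) and summarised under SAP 6.2.

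**The case against.** The best reply is that 9.1.4 does not amend Section 12. It says what a contact should ask and then sends the reader to Section 12, where 12.3.1 is mandatory and does not depend on attendance. Treatment given for an event after progression is covered by the last paragraph of Section 8, by Table 1, and by the 12.3.1 requirement to record measures used to manage events. On the medication reading of the closing phrase, only the mildest events are at issue.

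Much of this stands, and it limits the point to inconsistent wording rather than a missing safety rule. It does not remove the inconsistency: the pointer offers additional information after a specific, narrower script, and a site has no instruction on which prevails. The Section 8 reply concedes that two of its sentences conflict. The Amendment 3 log, used here only as context, records removal of the Grade 2 limit from Section 8, which suggests that the 9.1.4 wording is residual.

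A reader might infer several stronger things that the documents do not support:

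- **Event collection definitely stops at progression.** This is one of two readings.
- **The sickest subjects lose their post-treatment safety window.** Nothing says that those who miss the visit are the sickest, and serious events and deaths are still captured.
- **The combination arm is under-collected, pulling the comparison towards no difference.** Section 1.4 reports more deaths in that arm but no unexpected imbalance in on-treatment toxicity. There are no attendance data by arm, and a subject who has died is not reached by this contact.
- **A definite loss of 9 to 30 days, or a count of affected subjects.** The first needs the event reading and a last dose 0 to 21 days before progression, whereas dosing past progression, weekly daratumumab in Cycles 1 to 3 and long holds are all possible. The second needs proportions that the documents do not give.
- **All grades are required everywhere else.** Sections 12.4 and 12.5 are narrower.

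**Conclusion.** The point holds as a contradiction in operative text. The grade threshold in 9.1.4 conflicts with 12.3.1, and the progression stop for medication in 9.1.4 and Section 8 conflicts with Table 1 and with the last paragraph of Section 8; neither conclusion depends on how the closing phrase is read. A loss of non-serious events after progression depends on that phrase governing events. The practical effect assumes that sites followed 9.1.4 literally, which the documents do not show. It is confined to non-serious events among subjects assessed by contact, plus medication records after progression. Its direction and size between arms cannot be derived. It merits correction because the SAP presumes uniform capture, but it is not evidence that the safety comparison is biased.

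**What to change.** In 9.1.4, state that a subject who cannot attend is contacted to collect adverse events, and the medication used to treat them, over the Section 12 scope and window in force for that subject (12.3.1, or 12.4 or 12.5 once Amendment 6 or 7 applies), whether or not progression has occurred. A blanket all-grades instruction would itself contradict 12.4 and 12.5.

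In Section 8, reconcile the progression stop for adverse event and infusion-reaction medication with Table 1 and the section's last paragraph. The sentence on listed systemic medicines, which include corticosteroids, also stops at progression and should be settled at the same time.

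New wording cannot recover past data: the Amendment 7 rationale states that the database is locked, and 17.5 ends electronic data capture. For the study report, therefore, give by arm the number of subjects assessed by contact instead of a visit, and state which collection rule was applied.

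The cost is two wording changes, slightly more data at a contact that is already planned (where Section 12 still calls for it), and one short tabulation.
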